9.0 LABELING, PACKAGING, STORAGE AND RETURN OF CLINICAL SUPPLIES

9.1 Investigational Product

The investigator shall take responsibility for and shall take all steps to maintain appropriate records and ensure appropriate supply, storage, handling, distribution and usage of investigational product in accordance with the protocol and any applicable laws and regulations.

Clinical Supplies will be provided by the Sponsor as summarized in [Table 8](#).

Table 8 Product Descriptions

Product Name & Potency	Dosage Form
golimumab 50mg/0.5mL	Injection
placebo for golimumab 50mg/0.5mL	Injection

All placebos were created by the Sponsor to match the active product.

9.2 Packaging and Labeling Information

Clinical supplies will be affixed with a clinical label in accordance with regulatory requirements.

During Period 1 Open-label Run-in phase, subjects will receive open-label, kitted golimumab 50mg/0.5mL. Each kit will contain a single pre-filled syringe and each subject will receive 1 kit at the first dispensing visit followed by 3 kits at all subsequent dispensing visits. During Period 2 Double-blind, subjects will receive blinded, kitted golimumab 50mg/0.5mL or placebo. Each subject will be dispensed 2 kits every 2 months and each kit will contain 1 pre-filled syringe.

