5.2 Trial Treatment(s)

The treatments to be used in this trial are outlined below in [Table 1](#).

Table 1 Trial Treatment

Biologic	Dose/Potency	Dose Frequency	Route of Administration	Regimen (Treatment Period)	Use
Golimumab	Per approved label: 50 mg (or 100 mg)†	Every month (QM)	Subcutaneous (SC)	Open-label from Month 0 to Month 9 (Period 1); switch to open-label golimumab upon “flare” (Period 2)	Standard of Care
Golimumab (full-treatment regimen)	Per approved label: 50 mg (or 100 mg)†	Every month (QM)	Subcutaneous (SC)	Double-blind monthly injections of active golimumab for 12 months (or until “flare”)	Experimental
Golimumab (reduced-treatment regimen)	50 mg (or 100 mg)†	Every 2 months (Q2M)	Subcutaneous (SC)	Double-blind monthly injections of active golimumab, alternating with placebo for golimumab, for 12 months (or until “flare”)	Experimental
Matching placebo for golimumab		Every month (QM)	Subcutaneous (SC)	Double-blind monthly injections of placebo for golimumab for 12 months (or until “flare”)	Experimental
† For subjects with body weight more than 100 kg, increasing the dose of golimumab to 100 mg may be considered during the Open-label Period 1 (and would continue during Period 2, depending on the randomization schedule).					

The frequency of SC injections is monthly during the entire trial. After an initial dose has been given, administration then continues preferably on the same day of every month (consistent with approved labeling) with an allowed window of ± 5 days. As the trial progresses, the day of the month that is targeted for dosing can be re-set, if needed (see Section 7.1.1.10). Depending on the period of the trial (open-label Period 1 or double-blind Period 2) and on the randomization schedule for treatment withdrawal or continued treatment (during Period 2), an individual injection may contain active golimumab or a matching placebo.

The first dose of golimumab 50 mg SC is administered at the study center by site personnel on the day of enrollment at Visit 2 (considered “Month 0”). If allowed by local guidelines and after proper training in injection technique, subjects may self-inject if determined by their physician that it is appropriate and with medical follow-up as necessary. For subjects with a body weight of more than 100 kg, increasing the dose of golimumab to 100 mg SC may be considered; see Section 5.2.1.2.

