5.2.1.2 Dose Modification (Escalation)

For subjects with body weight more than 100 kg who, based on the investigator’s clinical judgment, do not achieve an adequate clinical response after up to 3 doses, increasing the dose of golimumab to 100 mg SC may be considered. This may require an unscheduled visit at Month 2 or Month 3, to enable a clinical evaluation by the investigator at that time for the decision to increase the dose to 100 mg SC. No other dose modifications for escalation are permitted during the trial. If a decision is made to increase to 100 mg (which requires 2 injections of 50 mg) for a given subject in Period 1, then administration of 2 injections at the time of each dose administration is also expected to continue for this subject through Period 2.

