During Period 2, eligible subjects will be randomly allocated to receive either a full regimen of golimumab (50 mg QM), a reduced regimen of golimumab (50 mg Q2M), or treatment withdrawal (placebo QM) in a double-blind manner. The blinded trial medication will be administered by the site personnel during the clinic visits, which are scheduled to occur every 2 months. If subjects are self-injecting at home, the monthly dose to be administered between the clinic visits will be dispensed.

Verbal and written instructions for proper storage, handling and administration of the trial medication will be given to subjects and will include instructions to contact the study site immediately if they experience problems with the trial medication administration.

Interruptions from the protocol specified treatment for ≥ 60 days require consultation between the investigator and the Sponsor and written documentation of the collaborative decision on subject management.

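### Sections 5.2 and 5.2.1.2 carry 100 mg (two injections per dose) into Period 2, while Section 7.1.1.9 names only 50 mg regimens and Section 9.2 states one syringe per monthly dose

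*Combined protocol and SAP*

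**What the plan says.** Two places carry the higher dose into Period 2.

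- Section 5.2.1.2 allows escalation for subjects over 100 kg with an inadequate response after up to 3 doses. It notes that a 100 mg dose takes two 50 mg syringes. For a subject so raised during the run-in, it says that "administration of 2 injections at the time of each dose administration is also expected to continue for this subject through Period 2".
- Table 1 in Section 5.2 lists 50 mg or 100 mg for open-label treatment and for both double-blind golimumab arms. Its footnote says that the increased dose may be considered in Period 1 "and would continue during Period 2, depending on the randomization schedule".

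Two places do not.

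- Section 7.1.1.9 describes the Period 2 allocation as "a full regimen of golimumab (50 mg QM), a reduced regimen of golimumab (50 mg Q2M") or placebo every month. It does not mention 100 mg.
- Section 9.2 states: "During Period 2 Double-blind, subjects will receive blinded, kitted golimumab 50mg/0.5mL or placebo". On quantity it says: "Each subject will be dispensed 2 kits every 2 months and each kit will contain 1 pre-filled syringe". For Period 1 it gives one single-syringe kit at the first dispensing visit and three at each later one. Neither sentence makes an exception for escalated subjects.

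Table 8 in Section 9.1 lists a single active strength, "golimumab 50mg/0.5mL", so there is no larger syringe that would deliver 100 mg in one injection.

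**The concern.** The two pairs of sections lead to different treatment of the same randomised subject.

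- **A site following 7.1.1.9 and 9.2** gives one 50 mg syringe a month to a subject who reached inactive disease on two.
- **A site following 5.2.1.2** gives two at a time. Unless the system issues more than 9.2 states, the interval's two kits are used at the clinic visit and none is left for the dose between visits.

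In the QM arm, the first path gives 50 mg monthly and the second gives 100 mg every second month, which is the Q2M timing. In the Q2M arm, Section 5.2.3 alternates active and placebo by month, so the two kits of one interval would be one of each. Using both together gives 50 mg at each clinic dose and loses the alternation.

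Golimumab exposure is the randomised variable, so this ambiguity sits in the treatment definition. Planned reporting may not make it plain. Section 8.11 defines compliance by doses taken over doses due, without saying whether one syringe of two counts as a dose. It also summarises injections, but states no expected number for 100 mg subjects. Section 8.12 ignores missing doses.

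**Working it through.** **Inputs**

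- Strength per syringe: 50 mg (Sections 9.1 and 9.2).
- Injections per dose: 1 at 50 mg, 2 at 100 mg (Section 5.2.1.2).
- Frequency: monthly throughout (Section 5.2), so 2 administrations per 2-month interval.
- Stated Period 2 supply: 2 kits per 2 months, 1 syringe each (Section 9.2).
- Period 2 dispensing visits: 24, 28, 32, 36, 40 and 44, six in all (Section 6.2).
- Stated Period 1 supply: 1 kit, then 3 per dispensing visit (Section 9.2). I read this as Visit 2, then Visits 4, 10 and 17 (Section 6.1).

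**Formula:** syringes per 2 months = (dose / 50 mg) × 2 administrations.

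**Period 2**

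| Dose | Needed per 2 months | Stated | Needed over six visits | Stated |
|---|---|---|---|---|
| 50 mg | 1 × 2 = 2 | 2 | 6 × 2 = 12 | 12 |
| 100 mg | 2 × 2 = 4 | 2 | 6 × 4 = 24 | 12 |

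The first row reproduces the plan's own figure exactly, so the stated kit count is the count for one 50 mg injection a month. At two injections per dose it covers 12/24 = 50%. This holds in every arm: 4 active per interval for QM, 2 active and 2 placebo for Q2M, and 4 placebo for withdrawal.

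The flow chart also marks an in-clinic administration at Visit 48. Counting it gives 13 doses and 13 × 2 = 26 syringes, against 12 stated, or 13 if one kit is assigned that day. The ratio is still at most half.

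**Period 1**

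Stated supply is 1 + 3 + 3 + 3 = 10 kits for the ten doses at Months 0 to 9, again one syringe per dose. A subject escalated at Month 3 has 7 doses left (Months 3 to 9) and needs 7 × 2 = 14 syringes against 7. A three-kit issue covers 3/2 = 1.5 doses at 100 mg.

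**How much could it matter to the primary comparison?**

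The documents do not give the share escalated. As an assumption only, 2% to 10% of an arm of 38 is 0.76 to 3.8, or about 1 to 4 subjects. Take the extreme: 4 affected in the golimumab arm, all of whom flare.

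- Planned 80% without flare becomes 34 × 0.80 / 38 = 71.6%. Against 30%, Table 7 puts power between 95% (at 70%) and 98% (at 75%).
- In the less favourable scenario, 75% becomes 34 × 0.75 / 38 = 67.1%. Against 40%, Table 7 puts power between 59% (at 65%) and 75% (at 70%), down from 88%.

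These are bounds under an assumed share and complete loss of effect. They are not estimates.

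**The case against.** The best defence is that Section 9.2 is a packaging summary and not a full supply schedule. It mentions no open-label kits for re-treatment after a flare and does not clearly cover the Visit 48 dose, yet nobody would conclude that those doses cannot be given. Section 5.2 promises all supplies in Table 1, which includes 100 mg. Section 7.1.1.9 promises Period 1 self-injectors enough medication to last until the next visit, and for Period 2 it speaks of the monthly dose, not of one syringe. Medication is assigned by IVRS/IWRS at each clinic visit (Section 6.2), and Section 7.1.5.1 refers to a user manual that may set kit counts by dose. Section 7.2.1 uses Section 5.2 as the dose reference for overdose.

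Much of this stands. A reader might infer that an escalated subject cannot receive the assigned regimen, or that the plan makes no provision at all for a second syringe. The documents do not support either, because the general supply text leaves room for extra kits. Nor does all Period 2 dosing text say 50 mg: Table 1 agrees with Section 5.2.1.2.

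The defence does not remove the conflict. None of these sections states a kit count for 100 mg subjects, says that paired syringes share blinded content, or qualifies the 50 mg wording in 7.1.1.9 or the each-subject rule in 9.2. The reference in 7.2.1 serves the overdose definition and is not a general rule of precedence.

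**Conclusion.** The inconsistency is real and lies in current text. For subjects raised to 100 mg, Sections 5.2 and 5.2.1.2 conflict with Sections 7.1.1.9 and 9.2, and the stated kit count is half of what two injections per dose require. The consequence that can be supported is that the same subject could be dosed differently depending on the section a site follows. In the Q2M arm the pairing of blinded syringes is also undefined.

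A reader might go on to infer that the mismatch adds flares to the golimumab arms and weakens the primary result. That is not shown. It needs subjects who weigh over 100 kg, respond inadequately at first, are escalated, and still meet the Month 4, 7 and 10 criteria, so the number is probably small. The documents give no count and no flare rate by dose. QM versus Q2M, where blurring would be most direct, is only exploratory (Section 8.6.1).

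A reader might also take one of the conflicting statements as the intended dose and call the other an error. The documents do not settle that. The case for correction rests on consistent dosing and blinding, not on power.

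**What to change.** Reconcile Table 1 and its footnote, Section 5.2.1.2, Section 7.1.1.9 and Section 9.2 so that all four state the same Period 2 dose for subjects raised to 100 mg in Period 1. The sponsor decides which rule stands.

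Then let supply follow from that rule:

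- State in Section 9.2 the number of kits per dispensing visit by current dose, and set the IVRS/IWRS assignment to match.
- If two syringes are used per dose, specify that both carry the same blinded content.
- Do the same for the Period 1 kit count, including supply at the unscheduled Month 2 or Month 3 visit at which escalation may be decided.

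The cost is protocol wording, an IVRS/IWRS setting and possibly a few extra kits. Sample size, visits and the analysis do not change.

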9.3 Clinical Supplies Disclosure

The emergency unblinding call center will use the randomization schedule for the trial to unblind subjects and to unmask treatment identity for the double-blind Period 2 of this trial. In the event that the emergency unblinding call center is not available for a given site in this trial, the central electronic randomization system (IVRS/IWRS) should be used in order to unblind subjects and to unmask treatment/vaccine identity. The Sponsor will not provide random code/disclosure envelopes or lists with the clinical supplies.

Treatment identification information is to be unmasked ONLY if necessary for the welfare of the subject. Every effort should be made not to unblind the subject unless necessary.

In the event that unblinding has occurred, the circumstances around the unblinding (e.g., date and reason) must be documented promptly, and the Sponsor Clinical Director notified as soon as possible. Only the principal investigator or delegate and the respective subject's code should be unblinded. Trial site personnel and Sponsor personnel directly associated with the conduct of the trial should not be unblinded.

9.4 Storage and Handling Requirements

Clinical supplies must be stored in a secure, limited-access location under the storage conditions specified on the label.

Receipt and dispensing of trial medication must be recorded by an authorized person at the trial site.

Clinical supplies may not be used for any purpose other than that stated in the protocol.

9.5 Discard/Destruction>Returns and Reconciliation

The investigator is responsible for keeping accurate records of the clinical supplies received from the Sponsor or designee, the amount dispensed to and returned, and the amount remaining at the conclusion of the trial. For all trial sites, the local country Sponsor personnel or designee will provide appropriate documentation that must be completed for drug accountability and return, or local discard and destruction if appropriate. Where local discard and destruction is appropriate, the investigator is responsible for ensuring that a local discard/destruction procedure is documented.

9.6 Standard Policies

Trial site personnel will have access to a central electronic randomization system (IVRS/IWRS system) to allocate subjects, to assign treatment to subjects and to manage the distribution of clinical supplies. Each person accessing the IVRS system must be assigned an individual unique PIN. They must use only their assigned PIN to access the system, and they must not share their assigned PIN with anyone.

10.0 ADMINISTRATIVE AND REGULATORY DETAILS

10.1 Confidentiality

10.1.1 Confidentiality of Data

By signing this protocol, the investigator affirms to the Sponsor that information furnished to the investigator by the Sponsor will be maintained in confidence, and such information will be divulged to the institutional review board, ethics review committee (IRB/ERC) or similar or expert committee; affiliated institution and employees, only under an appropriate understanding of confidentiality with such board or committee, affiliated institution and employees. Data generated by this trial will be considered confidential by the investigator, except to the extent that it is included in a publication as provided in the Publications section of this protocol.

10.1.2 Confidentiality of Subject Records

By signing this protocol, the investigator agrees that the Sponsor (or Sponsor representative), IRB/ERC, or regulatory authority representatives may consult and/or copy trial documents in order to verify worksheet/case report form data. By signing the consent form, the subject agrees to this process. If trial documents will be photocopied during the process of verifying worksheet/case report form information, the subject will be identified by unique code only; full names/initials will be masked prior to transmission to the Sponsor.

By signing this protocol, the investigator agrees to treat all subject data used and disclosed in connection with this trial in accordance with all applicable privacy laws, rules and regulations.

10.1.3 Confidentiality of Investigator Information

By signing this protocol, the investigator recognizes that certain personal identifying information with respect to the investigator, and all subinvestigators and trial site personnel, may be used and disclosed for trial management purposes, as part of a regulatory submissions, and as required by law. This information may include:

1. name, address, telephone number and e-mail address;
2. hospital or clinic address and telephone number;
3. curriculum vitae or other summary of qualifications and credentials; and
4. other professional documentation.

Consistent with the purposes described above, this information may be transmitted to the Sponsor, and subsidiaries, affiliates and agents of the Sponsor, in your country and other countries, including countries that do not have laws protecting such information. Additionally, the investigator's name and business contact information may be included when reporting certain serious adverse events to regulatory authorities or to other investigators. By signing this protocol, the investigator expressly consents to these uses and disclosures.

If this is a multicenter trial, in order to facilitate contact between investigators, the Sponsor may share an investigator's name and contact information with other participating investigators upon request.

10.1.4 Confidentiality of IRB/IEC Information

The Sponsor is required to record the name and address of each IRB/IEC member that reviews and approves this trial. The Sponsor is also required to document that each IRB/IEC meets regulatory and ICH GCP requirements by requesting and maintaining records of the names and qualifications of the IRB/IEC members and to make these records available for regulatory agency review upon request by those agencies.

10.2 Compliance with Financial Disclosure Requirements

Financial Disclosure requirements are outlined in the US Food and Drug Administration Regulations, Financial Disclosure by Clinical Investigators (21 CFR Part 54). It is the Sponsor's responsibility to determine, based on these regulations, whether a request for Financial Disclosure information is required. It is the investigator's/subinvestigator's responsibility to comply with any such request.

The investigator/subinvestigator(s) agree, if requested by the Sponsor in accordance with 21 CFR Part 54, to provide his/her financial interests in and/or arrangements with the Sponsor to allow for the submission of complete and accurate certification and disclosure statements. The investigator/subinvestigator(s) further agree to provide this information on a Certification/Disclosure Form, commonly known as a financial disclosure form, provided by the Sponsor or through a secure password-protected electronic portal provided by the

Sponsor. The investigator/subinvestigator(s) also consent to the transmission of this information to the Sponsor in the United States for these purposes. This may involve the transmission of information to countries that do not have laws protecting personal data.

10.3 Compliance with Law, Audit and Debarment

By signing this protocol, the investigator agrees to conduct the trial in an efficient and diligent manner and in conformance with this protocol; generally accepted standards of Good Clinical Practice (e.g., International Conference on Harmonization of Technical Requirements for Registration of Pharmaceuticals for Human Use Good Clinical Practice: Consolidated Guideline and other generally accepted standards of good clinical practice); and all applicable federal, state and local laws, rules and regulations relating to the conduct of the clinical trial.

The Code of Conduct, a collection of goals and considerations that govern the ethical and scientific conduct of clinical investigations sponsored by Merck, is provided in Section 12.1 - Merck Code of Conduct for Clinical Trials.

The investigator also agrees to allow monitoring, audits, IRB/ERC review and regulatory authority inspection of trial-related documents and procedures and provide for direct access to all trial-related source data and documents.

The investigator agrees not to seek reimbursement from subjects, their insurance providers or from government programs for procedures included as part of the trial reimbursed to the investigator by the Sponsor.

The investigator shall prepare and maintain complete and accurate trial documentation in compliance with Good Clinical Practice standards and applicable federal, state and local laws, rules and regulations; and, for each subject participating in the trial, provide all data, and, upon completion or termination of the clinical trial, submit any other reports to the Sponsor as required by this protocol or as otherwise required pursuant to any agreement with the Sponsor.

Trial documentation will be promptly and fully disclosed to the Sponsor by the investigator upon request and also shall be made available at the trial site upon request for inspection, copying, review and audit at reasonable times by representatives of the Sponsor or any regulatory authorities. The investigator agrees to promptly take any reasonable steps that are requested by the Sponsor as a result of an audit to cure deficiencies in the trial documentation and worksheets/case report forms.

The investigator must maintain copies of all documentation and records relating to the conduct of the trial in compliance with all applicable legal and regulatory requirements. This documentation includes, but is not limited to, the protocol, worksheets/case report forms, advertising for subject participation, adverse event reports, subject source data, correspondence with regulatory authorities and IRBs/ERCs, consent forms, investigator's curricula vitae, monitor visit logs, laboratory reference ranges, laboratory certification or quality control procedures and laboratory director curriculum vitae. By signing this protocol,

the investigator agrees that documentation shall be retained until at least 2 years after the last approval of a marketing application in an ICH region or until there are no pending or contemplated marketing applications in an ICH region or until at least 2 years have elapsed since the formal discontinuation of clinical development of the investigational product. Because the clinical development and marketing application process is variable, it is anticipated that the retention period can be up to 15 years or longer after protocol database lock. The Sponsor will determine the minimum retention period and notify the investigator when documents may be destroyed. The Sponsor will determine the minimum retention period and upon request, will provide guidance to the investigator when documents no longer need to be retained. The sponsor also recognizes that documents may need to be retained for a longer period if required by local regulatory requirements. All trial documents shall be made available if required by relevant regulatory authorities. The investigator must consult with and obtain written approval by the Sponsor prior to destroying trial and/or subject files.

ICH Good Clinical Practice guidelines recommend that the investigator inform the subject's primary physician about the subject's participation in the trial if the subject has a primary physician and if the subject agrees to the primary physician being informed.

The investigator will promptly inform the Sponsor of any regulatory authority inspection conducted for this trial.

Persons debarred from conducting or working on clinical trials by any court or regulatory authority will not be allowed to conduct or work on this Sponsor's trials. The investigator will immediately disclose in writing to the Sponsor if any person who is involved in conducting the trial is debarred or if any proceeding for debarment is pending or, to the best of the investigator's knowledge, threatened.

In the event the Sponsor prematurely terminates a particular trial site, the Sponsor will promptly notify that trial site's IRB/IEC.

According to European legislation, a Sponsor must designate an overall coordinating investigator for a multi-center trial (including multinational). When more than one trial site is open in an EU country, Merck, as the Sponsor, will designate, per country, a national principal coordinator (Protocol CI), responsible for coordinating the work of the principal investigators at the different trial sites in that Member State, according to national regulations. For a single-center trial, the Protocol CI is the principal investigator. In addition, the Sponsor must designate a principal or coordinating investigator to review the trial report that summarizes the trial results and confirm that, to the best of his/her knowledge, the report accurately describes the conduct and results of the trial [Clinical Study Report (CSR) CI]. The Sponsor may consider one or more factors in the selection of the individual to serve as the Protocol CI and or CSR CI (e.g., availability of the CI during the anticipated review process, thorough understanding of clinical trial methods, appropriate enrollment of subject cohort, timely achievement of trial milestones). The Protocol CI must be a participating trial investigator.

